11.3 Observational Endpoints

Observational endpoints will be summarized at all available time points at the time of analysis. Observational endpoints are supportive in nature and not intended to support additional claims. Data may be included in labelling per agreement with the FDA and will be limited to summary statistics (e.g. mean, standard deviation, minimum, median, maximum, number and percent) and will not include 95% confidence intervals or p-values. Statistical significance will be determined based on a two-sided p-value of 0.05. The p-values for the observational endpoints will not be adjusted for multiplicity and should be interpreted with caution.

11.3.1 To compare the mean improvement over baseline for QoL-7 between subjects randomized to treatment as compared to sham

Subjects Included in Analysis: All FAS subjects will be included in the analysis.

Endpoint(s): QoL-7 score. The score is calculated by assigning 1 for a yes response and 0 for a no response and summing over the 7 questions.

Statistical Analysis: An analysis will be performed using all available time points with complete follow-up at the time of the analysis. A generalized linear mixed model be used to compare average change in QoL-7 from baseline to follow-up between randomized groups over time on study. The dependent variable change in QoL-7 from baseline to follow-up with independent variables to include randomized group, follow-up time, baseline HDSS and two-way interaction terms. The covariance structure among the compound symmetric, auto-regressive and unstructured that provides the best model fit by the Schwarz BIC criterion will be chosen.

A hierarchical stepwise backward elimination technique will be used to reduce the model. The two-way interactions will be reviewed first, the two-way interaction with the largest p-value provided that p-value is greater than 0.05 will be removed from the model and the model refit and repeated until only two-way interactions with p-values < 0.05 are retained. The main effects for any two-way interaction retained in the model must remain in the model as well as the randomized treatment. That being said, the main effects will be evaluated in the same manner as the two-way interaction terms.

This analysis will be repeated for each of the 7 questions that comprise the QOL-7 and in the PP population.

11.3.2 To compare the proportion of patients with HDSS 1 or 2 at 4 weeks AND at least 50% improvement in GSP at 4 weeks over baseline between subjects randomized to treatment as compared to sham

Subjects Included in Analysis: All FAS subjects will be included in the analysis.

Endpoint(s): HDSS at follow-up. GSP % change at follow-up compared to baseline. will be calculated as in **Section 11.2.3.4**

Statistical Analysis: The proportion of patients with an HDSS of 1 or 2 at 4 weeks of follow-up AND at least 50% improvement in GSP at 4 weeks over baseline will be compared between treatment vs. sham using the Cochran-Mantel-Haenszel (CMH) test stratified by baseline HDSS value of 3 vs. 4 in the FAS population. Statistical significance is achieved with two-sided p-value <0.05 equivalent to one-sided p-value < 0.025. This analysis will be completed in the PP group as well.

11.3.3 To compare the proportion of patients with HDSS 1 or 2 at 4 weeks AND at least 75% improvement in GSP at 4 weeks over baseline between subjects randomized to treatment as compared to sham

Subjects Included in Analysis: All FAS subjects will be included in the analysis.

Endpoint(s): HDSS at follow-up. GSP % change at follow-up compared to baseline. will be calculated as in Section 11.2.3.4

Statistical Analysis: The proportion of patients with an HDSS of 1 or 2 at 4 weeks of follow-up AND 75% improvement in GSP at 4 weeks over baseline will be compared between treatment vs. sham using the Cochran-Mantel-Haenszel (CMH) test stratified by baseline HDSS value of 3 vs. 4 in the FAS population. Statistical significance is achieved with two-sided p-value <0.05 equivalent to one-sided p-value < 0.025. This analysis will be completed in the PP group as well.

11.3.4 To compare the duration of efficacy between subjects randomized to treatment as compared to sham

Subjects Included in Analysis: All FAS subjects will be included in the analysis.

Endpoint(s): HDSS

Statistical Analysis: A Kaplan-Meier product limit method will be used for the analysis. Time 0 will be the treatment date. For subjects who do not respond to treatment, the duration of treatment will be 0. For subjects who do respond to treatment, the event is the first subsequent week of follow-up after the 4 week follow-up in which the subject reported an HDSS of 3 or 4 or censoring from the study either due to drop-out or completing the study without reverting to HDSS 3 or 4. The study groups will be compared using the Log-Rank statistic stratified by HDSS 3 or 4 at baseline.

This analysis will be completed for reversion to the patient's baseline value and in the PP group as well.

11.3.5 To compare mean change from baseline at 4 weeks in GSP between subjects randomized to treatment as compared to sham.

Subjects Included in Analysis: All FAS subjects will be included in the analysis.

Endpoint(s): The average of 2 accurate GSP measurements will be conducted for each Axilla at each time point. The total sweat production at each timepoint will be calculated by summing the average sweat production from both axilla. The change in GSP at 4 weeks will be calculated by subtracting the total sweat production at baseline from the total value at 4 weeks.

Statistical Analysis: An analysis of variance model will be used to compare average change in total GSP at 4 weeks as compared to baseline between randomized groups. The dependent variable is change in total GSP at 4 weeks as compared to baseline with independent variables to include randomized group, baseline HDSS, and two-way interaction terms.

A hierarchical stepwise backward elimination technique will be used to reduce the model. The two-way interactions will be reviewed first, the two-way interaction with the largest p-value provided that p-value is greater than 0.05 will be removed from the model and the model refit and repeated until only two-way interactions with p-values < 0.05 are retained. The main effects for any two-way interaction retained in the model must remain in the model as well as the randomized treatment. That being said, the main effects will be evaluated in the same manner as the two-way interaction terms. This analysis will be repeated in the PP population.

11.3.6 To compare responses to additional QOL questions from baseline throughout follow-up, as appropriate between subjects randomized to treatment as compared to sham.

Subjects Included in Analysis: All FAS subjects will be included in the analysis.

Endpoint(s): The responses to the following questions:

Baseline and follow-up: My underarm odor bothers me (Not at all, a little bit, a moderate amount, a great deal, an extreme amount).

2 and 4 weeks only: I would recommend this treatment to another person (y/n).

Follow-up only: I can wear clothes that I want to wear (y/n),

Statistical Analysis: These data will be summarized by number and percent in each category by randomized group and follow-up. The data will be summarized in the PP population as well.

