The N-SWEAT patch (previously called the CDX-101 Patch) was studied in a feasibility study in which 12 subjects (both axillae) were successfully treated; 4 of these subjects received an optional (both axillae) retreatment procedure after the initial study period. Thus, a total of 32 Patches were used during this study: 24 in the initial treatments and 8 during the retreatments. Technical feasibility of heat generation was demonstrated across all treatments. The safety endpoint of the study was also met in all patients. There were no serious adverse events (SAEs) reported in the study. Only two (2) device related adverse events were reported; both were deemed mild. Efficacy as measured by a 1-point improvement in HDSS was observed in 91% (11/12) subjects, 64% of the subjects achieved HDSS scores of 1 or 2 at the end of the evaluation period (6-weeks). Mean gravimetric sweat production was reduced an average of 68% across the 6-week follow-up period. QoL survey results showed a consistent trend with the majority of subjects reporting improvement across all measures. Device tolerability was confirmed with all subjects reporting an acceptable level of pain during the procedure.

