The outcomes of the STAYDRI.1 Study led the company to the decision to initiate a pilot study with a control group (STAYDRI.A). STAYDRI.A was a prospective, randomized, controlled, double-blinded pilot study, conducted under IRB approval with a non-significant risk designation. Sixteen (16) subjects were successfully randomized (1:1) and treated bilaterally, with both axillae receiving the same treatment; 8 subjects (16 axillae) with the N-SWEAT patch and 8 subjects (16 axillae) with the sham patch. Subjects and evaluating clinicians were blinded to the assigned treatment. The device was shown to be safe with only one (1) device-related AE observed in the N-SWEAT treatment group; the AE was deemed moderate and resolved without sequelae. There were no serious adverse events (SAEs) reported during the study. The efficacy endpoints of the study were also successful. Subjects treated with the N-SWEAT patch demonstrated consistent and sustained improvement in HDSS and additional QoL measurements. A post hoc analysis demonstrated a statistically significant difference in subjects with a 2-point improvement in HDSS between the treated and sham groups, 67% vs 0% respectively at 4-weeks ($p=0.0123$). Further, 83% of treated subjects reported a HDSS score of 1 or 2 at 4-weeks versus 0% in the sham control ($p=0.0032$). Moreover, improvements in both level of "bother" and "impact on daily living" were sustained throughout the study with the difference in QoL scores between the treated and sham groups increasing over the follow-up period. Finally, at the end of the study

CANDESANT BIOMEDICAL	CLINICAL STUDY PROTOCOL SAHARA STUDY	Document #: CB-CLP-001 Revision: E
---------------------------------	---	---------------------------------------

(6-weeks) 66.7% of N-SWEAT treated subjects demonstrated a reduction in GSP that was $\geq 50\%$. Interestingly, subjects treated with the sham also exhibited a reduction in GSP (mean 44% / median 46% / $\geq 50\%$ reduction 14%). It is important to note that subjects treated with the sham did not have corresponding improvements in the QoL assessments as measured by either HDSS or any of the QoL questionnaires. This finding, while on the surface contradictory, is consistent with recent published reports that gravimetric sweat production may not be clinically meaningful in determining the level of disease.

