8.3 Baseline Assessment

8.3.1 Prior to Enrollment

No more than 14 days after the screening visit the subject will report for baseline assessment and potential treatment. (*NOTE: If axillary hair was clipped at the screening visit, the baseline visit must be at least 72 hours later*). All efforts should be taken to make sure that the subject is prepared to undergo treatment during this visit if they meet the eligibility requirements below.

Baseline Assessments include:

- **GSP:** Gravimetric sweat production should be measured in accordance with the instructions and training provided by the sponsor (**Appendix D**). Any deviation from this procedure should be documented and explained.
 - At baseline, subject GSP assessment is required to show at least 50 mg /5min of spontaneous resting axillary sweat production in each axilla and no more than 300 mg/5 min in either axilla. The difference between screening and baseline for either axilla may not be >100%.
- **HDSS:** The Hyperhidrosis Disease Severity Scale should be explained to the subject in plain language and in accordance with the instructions and training provided by the sponsor (**Appendix A**). It must be clear that these questions relate to underarm sweating.
 - Subject HDSS score must be 3 or 4

CANDESANT BIOMEDICAL	CLINICAL STUDY PROTOCOL SAHARA STUDY	Document #: CB-CLP-001 Revision: E
-------------------------	---	---------------------------------------

- **Physical Exam:** The subject must be in good general health and able to independently assess their sweating in a reasonable way.
- **Assessment for Local Skin Reactions:** The investigator will evaluate axillary application sites for any skin irritation. If present (greater than 1) based on the Skin Erythema Assessment and the Clinical Signs/Symptom Descriptors (**Appendix B**), the subject may only be treated after the issue has been resolved (less than or equal to 1).
 - **NOTE:** *If abrasions or broken skin are present; the subject may report back for re-screening after the skin has had time to heal (at least 72 hours). Treatment in the study in the presence of skin irritations or abrasions can lead to increased probability of the patient experiencing discomfort, pain or skin irritations.*
 - **NOTE:** The subject must meet the criteria above in both axilla since the study treatment includes treatment of both axillae in the same procedure.

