4. SAMPLE SIZE AND POWER CONSIDERATIONS

The primary effectiveness evaluation is driving the randomized sample size for the trial. The maximum of two scenarios considered required 50 evaluable subjects per randomized group at 4 weeks of follow-up. Increasing that number for up to 10% attrition requires 55 randomized subjects per group or 110 randomized subjects. This number provides at least 80% power for the primary efficacy objective at the two-sided 0.05 significance level.

The trial is also designed to enroll a roll-in cohort of N=10 treatment subjects at one investigational center prior to randomizing any subjects in the trial.

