A hierarchical stepwise backward elimination technique will be used to reduce the model. The two-way interactions will be reviewed first, the two-way interaction with the largest p-value provided that p-value is greater than 0.05 will be removed from the model and the model refit and repeated until only two-way interactions with p-values < 0.05 are retained. The main effects for any two-way interaction retained in the model must remain in the model as well as the randomized treatment. That being said, the main effects will be evaluated in the same manner as the two-way interactions. This analysis will be completed in the PP group as well.

11.2.3.4 To estimate the proportion of subjects randomized to treatment with at least 50% improvement from baseline to 4 weeks in gravimetric sweat production (GSP)

Subjects Included in Analysis: All FAS subjects randomized to receive the N-SWEAT patch.

Endpoint(s): The average of 2 accurate GSP measurements will be conducted for each Axilla at each time point. The total sweat production at each timepoint will be calculated by summing the average sweat production from both axilla. The percentage change at 4 weeks will be calculated based on the total sweat production at baseline and 4 weeks.

Statistical Analysis: The potential confounding factors of room temperature, room humidity , position during evaluation and time of evaluation will be summarized for baseline and 4 weeks. The difference in temperature, humidity, time of evaluation and whether or not the baseline and 4 week evaluation were performed in the same or different position will be summarized. These factors will be evaluated with respect to their relationship with the endpoint and association with outlying values, if any, using graphical techniques and summary statistics. Depending on this evaluation, outlying values may be excluded from the analysis with justification provided and relationships, if any found, will be summarized.

The proportion of patients with 50% or greater improvement from baseline to 4 weeks will be statistically compared to zero by calculating the Wilson's 95% two-sided confidence interval and comparing the lower bound to zero. If the lower bound is greater than zero, there is statistically

significant evidence that the proportion of subjects with a clinically relevant improvement exists and is greater than 0. This analysis will be completed in the PP population as well.

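### SAP 11.3.5, the only between-arm test of continuous GSP, omits baseline GSP from the model despite a roughly six-fold eligible range; adding it is a cheap, minor gain

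*SAP*

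**What the plan says.** SAP 11.3.5 sums the two axillae at each visit and forms the difference in mg: "The change in GSP at 4 weeks will be calculated by subtracting the total sweat production at baseline" from the week-4 total. An analysis of variance then compares the arms, with randomised group, baseline HDSS and two-way interactions as independent variables. Backward elimination at 0.05 follows, and among the main effects only randomised group is protected unconditionally. Baseline GSP is not listed.

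Elsewhere the plan treats GSP response as proportional. For secondary endpoint 4 (SAP 11.2.3.4), "The percentage change at 4 weeks will be calculated based on the total sweat production at baseline and 4 weeks", with a 50% threshold. The composites in SAP 11.3.2 and 11.3.3 use 50% and 75% thresholds together with HDSS. Protocol 3.3 gives earlier results in percent: in the feasibility study, "Mean gravimetric sweat production was reduced an average of 68% across the 6-week follow-up period"; in the controlled pilot, "subjects treated with the sham also exhibited a reduction in GSP (mean 44% / median 46" percent).

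Protocol 8.3.1 requires "at least 50 mg /5min of spontaneous resting axillary sweat production in each axilla and no more than 300 mg/5 min in either axilla".

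For all observational endpoints, SAP 11.3 states: "Statistical significance will be determined based on a two-sided p-value of 0.05". It makes no multiplicity adjustment, describes these endpoints as not supporting claims, and keeps their p-values out of labelling.

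**The concern.** Secondary endpoint 4 is single-arm and tested against zero, and the two composites combine GSP with HDSS. That leaves SAP 11.3.5 as the only randomised comparison of the objective measure by itself. It matters because sham subjects in the pilot also showed a large fall in GSP, so only a comparison with sham can show whether the patch reduces measured sweat further.

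With 50 to 300 mg allowed per axilla, the total can run from about 100 to 600 mg. A 60% fall is then 60 mg in one subject and 360 mg in another. Without baseline GSP in the model, that variation goes into the residual and obscures the arm difference. Baseline HDSS, with only two levels among eligible subjects, cannot be assumed to stand in for it.

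**Working it through.** **The plan's own figure.** No power, SD or effect size is stated for GSP. The only sample-size figure is for HDSS: "The maximum of two scenarios considered required 50 evaluable subjects per randomized group at 4 weeks of follow-up". The pooled two-proportion formula, 80% power, two-sided 0.05, reproduces it closely:
- 85% vs 60%: (1.96·√(2·0.725·0.275) + 0.842·√(0.85·0.15 + 0.60·0.40))² / 0.25² = 48.9, so 49 (stated 50).
- 73% vs 44%: the same formula gives 44.1, so 45 (stated 45).
- Attrition: 50 × 1.10 = 55, agreeing with "up to 10% attrition requires 55 randomized subjects per group or 110 randomized subjects".

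So 50 per arm is used below.

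**Inputs for GSP.** From the documents: mean ratios (week 4 to baseline) of 0.32 active (68% reduction, feasibility study) and 0.56 sham (44% reduction, pilot). Assumed: lognormal ratios with log SD 0.5, 0.7 or 0.9; total baseline with mean 248 and SD 100 mg (a lognormal truncated to 50–300 mg per axilla).

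**Why the covariate helps.** Change is D = B(R − 1), where B is baseline and R the ratio with mean m. Within an arm

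Var(D) = (1 − m)²·Var(B) + Var(R)·E(B²), with Var(R) = m²(e^(s²) − 1).

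The first term is baseline size. Fitting B with a common slope of −0.56 (midway between −0.68 and −0.44) reduces (1 − m)² to 0.12² in each arm.

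Numbers: E(B²) = 248² + 100² = 71,504. The arm difference is 0.24 × 248 = 59.5 mg. The baseline term summed over arms is (0.68² + 0.44²) × 10,000 = 6,560 unadjusted and 2 × 0.12² × 10,000 = 288 adjusted. Power ≈ Φ(59.5/SE − 1.96), with SE = √(sum of variances / 50).

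| log SD | ratio term, active + sham | SE as written → adjusted | power as written → adjusted |
|---|---|---|---|
| 0.5 | 2,080 + 6,369 | 17.3 → 13.2 | 93% → 99% |
| 0.7 | 4,630 + 14,179 | 22.5 → 19.5 | 75% → 86% |
| 0.9 | 9,137 + 27,983 | 29.6 → 27.4 | 52% → 59% |

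**Simulation, no measurement error.** Power goes from about 97/80/59% to >99/91/68%. Other runs under similar assumptions gave 91–95/75–78/53–58% as written and >99/90–91/65–69% adjusted.

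**Simulation, additive error on the total.**
- 10 mg: 73% → 89% (SD 0.7); 55% → 66% (SD 0.9).
- 30 mg: 93 → 99%, 75 → 87%, 53 → 63% (SD 0.5, 0.7, 0.9).
- 60 mg, median ratios 0.40 vs 0.54, SD 0.5: 49% → 61% with uniform baselines, 41% → 50% with lognormal.

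**Where it does not help.** With a constant mg effect (130 vs 90 mg, SD 60), power is 91% → 90% with uniform baselines and 89% → 89% with lognormal. With smaller effects and wide spread (ratios 0.60 vs 0.80, SD 0.7, uniform baselines) it is 40.5% → 40.4%. So the covariate gains nothing in some settings, but no run showed a loss beyond simulation error.

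**Does the scale matter as well?** The log ratio with log baseline reaches >99/97/86% with no error. At 60 mg error it falls below the plan as written: 72 vs 81%, 56 vs 64% and 39 vs 45%. With 3% zero readings floored at 0.1 mg it gives about 61/56/51%, against 92/77/54% as written.

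**The case against.** The strongest objection is low stakes. The endpoint is observational, supports no claim, and plays no part in study success. The pilot discussion in Protocol 3.3 itself doubts that GSP is clinically meaningful. All of this stands and sets the severity.

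The plan also has some flexibility. SAP 8.1 lists GSP among the baseline characteristics and allows covariates that differ between arms at 0.05 to be evaluated, extending to observational endpoints if desired. SAP 1 permits transformations when the distribution is unsuitable. Neither is a commitment. The first depends on a chance imbalance, whereas the precision gain does not; the second leaves the choice until the data are seen.

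The effect size is cross-study: 68% comes from a single-arm feasibility study averaged over six weeks, 44% from another study's sham arm of eight randomised subjects at six weeks. The size of the gain is therefore illustrative.

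A reader might infer something stronger: that the mg scale itself costs substantial power and should give way to a log ratio. The documents do not support that. They give no GSP variability, measurement error or frequency of near-zero readings, and the ranking of the scales reverses within plausible ranges of these. Nor can the pilot settle it. For example, a sham arm with median ratio 0.54 and log SD 0.25 strongly favours the log ratio, but implies Φ(ln(0.50/0.54)/0.25) = 38% of sham subjects with at least a 50% fall, where the protocol reports 14%. Protocol 9.10.3 also names mean change at 4 weeks as the endpoint, and a ratio of geometric means would be a different quantity.

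**Conclusion.** The point holds, at minor severity. SAP 11.3.5 leaves out a baseline measurement that is already collected and that, under a proportional effect, explains part of the outcome's variance. At 50 per arm the simulated gain is about 3, 11 and 9 points at log SD 0.5, 0.7 and 0.9. It rests on the assumed SDs, the assumed baseline distribution and the cross-study effect; under a constant mg effect it is essentially nil. The covariate leaves the estimated quantity, a difference in mean mg change, unchanged. The mismatch between an mg test and a percent response criterion is real, but it justifies a supporting analysis, not a change of the main scale.

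**What to change.** In SAP 11.3.5:
- Add baseline total GSP as a covariate (main effect). State that it, randomised group and baseline HDSS stay in the model and are not subject to backward elimination.
- Prespecify one supporting between-arm comparison on percent change or the log ratio. If the log ratio is chosen, state the rule for zero and near-zero readings.
- Keep the mg comparison as the stated analysis.

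Make the change before the 4-week analysis, when SAP 7 unblinds the sponsor. The cost is two or three sentences of SAP text and one amended table shell, with no new data, visits or subjects. The covariate uses one residual degree of freedom.
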